3.5 Non-Disposable Component-Data Acquisition System

The Neurapheresis System utilizes PC and data acquisition system. The system operates with customized software for the user interface, data logging (archive, analysis and data transfer), motor control, pressures and flow rate monitoring. This system software is considered investigational and is not commercially available. The figure below provides a visual of the touch screen user interface.

[figure not shown]

Figure 5: Neurapheresis System Touch Screen User Interface

The system has an integrated battery back-up for use during transport or a systemic power loss at a center. When not in use, the cart shall be connected to a power supply in the identified center storage area.

3.6 Shipping and Device Accountability of the Investigational System

The investigational catheter and non-disposable components of the Neurapheresis System will be shipped and tracked in accordance with 21CFR§812.140 (b)(2) requirements. and will only be shipped to sites and Investigators who have been selected by MNeuro to participate in this study.

A Device Accountability Log will be maintained to catalogue receipt and disposition of the catheter and non-disposable components. The Sponsor will provide a shipping mechanism or instructions for return of the system and individual components as needed through completion of the clinical study.

3.6.1 Required Disposable Component Return

The Neurapheresis system catheter is the only disposable that is required to be returned to the Sponsor. While the guidewire is considered to be investigational due to their off-label use, they may be destroyed at the study site. The MNeuro Clinical Field Specialist (CSF) (i.e. technical representative) has the discretion to request return of other disposable components if there is a performance question that could be answered by further analysis. Catheters or other used disposables are to be returned to the Sponsor in the biohazard shipping containers provided. Returns of any components will be documented on the Device Accountability Log.

4. STUDY DESIGN

The PILLAR-XT study is a prospective, multi-center, non-randomized single arm study that is an extension of the first-in human PILLAR study.

4.1 Objective

The objective of this study is to further demonstrate safety and characterize effectiveness of the Neurapheresis™ System (extracorporeal system and catheter) to remove red blood cells (RBCs) and lysed blood by-products from hemorrhagic cerebrospinal fluid (CSF) following aneurysmal subarachnoid hemorrhage (aSAH).

4.2 Scale and Duration

The Study will enroll N=30 “Treated” subjects, as defined by the protocol. The study will be performed at up to 8 centers within the United States. Subjects will have assessments and data collection at enrollment, during catheter placement and Neurapheresis procedure, 2 days (± 1 days), at Neuro ICU discharge and 30 days (± 3 days) post removal of the catheter.

Based on the incidence of occurrence of SAH in the US population, it is estimated that it will take approximately 12-16 months to complete enrollment and protocol required data collection, analysis and reporting requirements.

4.3 Study Endpoints

The PILLAR-XT Study does not have a hypothesis based statistical endpoint due to the feasibility nature of the investigation.

Primary Endpoints:

1. Mean reduction of cisternal blood via CT post study therapy
2. Proportion of subjects with Neurapheresis Catheter, System or Therapy related serious adverse events

Secondary Safety Endpoints:

- Proportion of subjects with successful catheter placement of those attempted
- Proportion of subjects with study device or therapy related adverse events
- Proportion of subjects with systemic CNS infection within 5 day of catheter removal

Secondary Efficacy endpoints:

- Mean reduction of RBCs and total protein by CSF sample post study therapy
- Mean length of Neuro ICU stay

Exploratory endpoints:

- Proportion of subjects requiring additional CSF management during study therapy or on-going CSF management post study therapy
- Reduction in biomarkers of inflammation as seen in CSF, blood and physiologic manifestations post study therapy
- Proportion of subjects with symptomatic complications from aSAH
- Analysis of endpoints by the following sub-groups for any groups that have at least 5 subjects that meet the criteria for the group;
 - Age: <45, ≥ 45 -<60, 60 – 70 years

- Gender: male, female
- Enrollment Modified Fischer grade: 2, 3, 4
- Baseline cisternal Hijdra score: ≤15, 16-20, 21-25, 26-30
- Neurapheresis time: <16hrs, ≥16-28hrs, >28-40hrs, >40hrs
- Other sub-groups not yet defined

4.4 Justification for Study and Design

The previous first-in-human study, PILLAR study, was completed to substantiate the feasibility and safety of Neurapheresis in aneurysmal SAH patients. As described in section 2.1, the study endpoints were met. The PILLAR-XT study is designed to further confirm safety and characterize efficacy of Neurapheresis therapy. Additionally, this study is expected to generate foundational data for development of the Neurapheresis treatment curve (e.g. time or volume processed needed to clear blood from the subarachnoid cisterns and lumbar spine). The study works in tandem with the current SOC treatments for SAH and does not detract from the established care pathways, or deny enrolled subjects proven therapies. The PILLAR-XT study utilizes the established skill sets of chosen Investigators who are already trained in the treatment and care of SAH patients and insertion/management of lumbar drains.

5. SUBJECT SELECTION

5.1 Study Population and Eligibility

Subjects considered for the PILLAR-XT study will be identified from a pool of patients, who are admitted to the investigational center and have experienced a SAH. Subjects will be eligible for enrollment based on adherence to the inclusion/exclusion criteria outlined below. The Investigator and/or designated site staff is responsible for screening patients to determine the appropriateness of the PILLAR-XT study for each patient based on compliance to study criteria and the overall patient status.

5.2 Screening and Subject Enrollment

Screening for potential study subjects can be done either prior to or after aneurysm securement depending on the institutional work flow, IR/OR availability, LAR availability or patient status. Inclusion or exclusion criteria that can be assessed by institutional SOC may be done so prior to written informed consent, however no study specific procedures may be performed until informed consent is obtained. Informed consent is considered the point of enrollment.

5.3 Institutional Standard of Care Treatment

The PILLAR-XT study does not require a uniform method for the treatment to secure the aneurysm i.e., Clip vs. Coil. Additionally, the Investigator may use accepted institutional SOC and professional discretion for interventions and treatments which include, but are not limited to:

- SOC neurological assessments
- SOC imaging
- ICP monitoring
- EVD placement
- “Triple H” therapy (hypertension, hypervolemia, hemodilution)

- Hyperventilation
- Nimodipine
- Seizure prophylaxis
- Antimicrobial prophylaxis

5.4 Inclusion Criteria

Subjects who meet all of the following criteria may be given consideration for inclusion in this clinical investigation:

- Age: 18 – 70 years
- Informed consent by the patient or his/her legally authorized representative
- Modified Fisher Grade 2, 3 or 4 SAH
- Hunt & Hess I-IV
- First aneurysmal SAH that has been confirmed by CT scan and secured or planned securement via clipping or coiling per institutional SOC
- Patient is \leq 48 hours post bleeding event
- World Federation of Neurosurgeons (WFNS) Grades I-IV
- Patient is indicated for a ventriculostomy

5.5 Exclusion Criteria

Subjects who meet any of the following criteria will be excluded from this clinical investigation:

- Pregnancy
- Patients with a SAH due to mycotic aneurysm or AV malformation
- Patients who present with an acute MI or unstable angina
- Patients with uncontrolled diabetes at the time of catheter placement
- Patients who present with a creatinine $> 2.0\text{mg/dl}$
- Imaging demonstrates supratentorial mass lesions $\geq 15\text{ cc}$
- Imaging demonstrates $\geq 2\text{ mm}$ of mid-line-shift associated with infarction and or edema
- Imaging demonstrates infratentorial mass lesion $\geq 10\text{cc}$
- Imaging demonstrates presence of any subdural hematoma
- Effacement of the basilar cisterns (suprasellar, ambient, chiasmatic and quadrigeminal)
- Vasospasm on admission as defined by angiographic evidence
- Patients with a coagulopathy that cannot be reversed per the professional discretion of the investigator
- Patients with a connective tissue disorder that may impact the integrity of the dura
- Thrombocytopenia def. platelet count $< 100,000$
- Patients on low molecular weight heparin, such as Lovenox
- Patients on Clopidogrel bisulfate (Plavix) or other chronic platelet inhibitors
- Patients with a documented history of cirrhosis
- Non-communicating obstructive hydrocephalus
- Patients with a lumbar or thoracic spinal anatomy (e.g. severe spinal stenosis) or history of posterior fusion hardware that would interfere with placement or appropriate in-dwelling of the catheter
- Existing hardware that prevents accurate CT imaging
- Pre-existing Lumbar Drain
- Local skin infections or eruptions over the puncture site
- Signs of CNS infection, sepsis or pneumonia
- Lumbar puncture within 6 hours

- Concurrent participation in another study which is not observational or retrospective in nature without prior approval from the Sponsor

5.6 Informed Consent

The Sponsor will provide to each center, an FDA approved Informed Consent Form (ICF) template which may be edited to include center specific language or compliance requirements. The Sponsor and Institutional Review Board (IRB) must approve any changes to the form prior to use for consent of a patient. A central IRB, Western IRB (WIRB), will be utilized for this study. Each enrolled subject must also consent to data transfers affected by HIPAA; the center may use their own HIPAA consent form to document this data transfer.

Informed Consent is a process by which a patient voluntarily confirms their willingness to participate in the study after being informed of all risks and requirements. Informed Consent is documented by means of a signed and dated ICF. Once the patient or their legally authorized representative (LAR) signs and dates the ICF, the patient is considered enrolled in the study and becomes a study subject.

Study enrollment without consent must be reported by Minnetronix, to the IRB and the FDA. Any violations of the informed consent process must be reported as deviations to the sponsor and local regulatory authorities as appropriate.

The process of obtaining Informed Consent shall:

- Process of obtaining Informed Consent must be documented in the Subject's medical record or study binder,
- Be conducted by the Principal Investigator or designee authorized to obtain informed consent,
- Include a description of all aspects of the clinical study that are relevant to the patient's decision to participate throughout the clinical study,
- Avoid any coercion of or undue influence of patient to participate,
- Not waive or appear to waive patient's legal rights,
- Use native language that is non-technical and understandable to the patient or his/her legal representative,
- Provide ample time for the patient or LAR to consider participation and ask questions if necessary,
- Ensure important new information is provided to new and existing Subjects throughout the clinical study.

The ICF shall always be signed and personally dated by the subject or LAR and by the Investigator or an authorized designee responsible for conducting the Informed Consent process. If a LAR provides signatory authority, the subject shall be notified of the informed consent and study participation as soon as his/her medical condition allows. The original signed ICF will be retained by the center and a copy of the signed and dated document and any other written information must be given to the subject or LAR signing the form.

If new information becomes available that can significantly affect a subject's future health and medical care, that information shall be provided to the affected subject(s) in written form via an amended informed consent form or other format as requested by the IRB or FDA. Further, if requested by the IRB or FDA, all affected subjects shall be asked to confirm their continuing informed consent in writing.

Other situations may necessitate revision of the ICF, e.g., amendments to the protocol, a change in Principal Investigator, administrative changes or requests following annual review by the IRB.

The new version of the ICF must be approved by the IRB and Minnetronix before implementation at investigative centers. The IRB will determine the subject population to be re-consented, if applicable.

Once the patient or their LAR provides consent, data collection may begin. The Investigator shall continue the institutional SOC for the treatment of SAH while providing the Sponsor with the data required for the study.

5.7 Subject ID Assignment and Enrollment Notification

Once Centers have identified a study candidate and Informed Consent has been obtained, the Sponsor must be notified as soon as possible to ensure rapid deployment of the Sponsor's Technical Personnel. Specific instructions on the study communication/notification process will be covered at site specific training. Subject ID's will be assigned via the study database and documented on a screening log.

5.7.1 Subject Enrollment Classifications

All patients who provide written consent to participate in the study will be considered enrolled study subjects, however not all subjects will contribute to the enrollment cap of N=30 Treated Subjects. Only treated subjects, as defined below, will contribute to the enrollment cap. As such, it is expected that up to 40 subjects may be enrolled to meet the enrollment cap. FDA, IRBs and Investigational sites will be notified when enrollment is complete.

Intent to Treat Subjects:

- Subjects who provide written informed consent but do not have placement of the study catheter attempted. This would include placement tools such as the epidural needle and guidewire. Intent to Treat subjects will be exited immediately. They will not count towards the enrollment cap of N=30 treated subjects. Only enrollment and study exit data will be collected in the study database.

Attempt to Treat Subjects:

- Subjects who provide written informed consent and have any portion of the catheter placement procedure attempted (including the epidural needle and guidewire) but placement was unsuccessful. Attempt to Treat subjects will be followed through 2 days post-attempt for safety then will be exited. They will not count towards the enrollment cap of N=30 treated subjects. They will be included in the analysis of safety endpoints but will not be included in the analysis of efficacy endpoints. Enrollment, catheter placement attempt, 2 day follow-up and study exit data will be collected along with any adverse events or protocol deviations if applicable.

Treated Subjects:

Subjects who provide written informed consent, have successful placement of the study catheter and had Neurapheresis initiated. These subjects will be followed out to 30 days according to the study protocol then exited. They will count towards the enrollment cap of

N=30 treated subjects and used in all analyses. All study data through the 30 day follow-up will be collected.

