Enrollment Categorization	All patients who provide written consent to participate in the study will be considered enrolled study subjects, however not all subjects will contribute to

	
the enrollment cap of N=30 treated subjects. Only “Treated” subjects, as defined below, will contribute to the enrollment cap. As such, it is expected that up to 40 subjects may be enrolled to meet the enrollment cap of N=30 Treated Subjects.
 
Informed consent may be obtained prior to or after aneurysm securement as able based on patient status upon admission and legally authorized representative (LAR) availability if needed.
 
Intent to Treat Subjects:
 
 Subjects who provide written informed consent but do not have placement of the study catheter attempted. This would include placement tools such as the epidural needle and guidewire. Intent to Treat subjects will be exited immediately as they have not received any portion of the study catheter or study therapy. They will not count towards the enrollment cap of N=30 treated subjects. 
Attempt to Treat Subjects:
 
 Subjects who provide written informed consent and have any portion of the catheter placement procedure attempted (including the epidural needle and guidewire) but placement was unsuccessful. Attempt to Treat subjects will be followed through 2 days post-attempt for safety then exited. They will not count towards the enrollment cap of N=30 treated subjects. They will be included in the analysis of safety endpoints but will not be included in the analysis of efficacy endpoints. 
Treated Subjects:
 
 Subjects who provide written informed consent, have successful placement of the study catheter and have study therapy initiated. These subjects will be followed out to 30 days according to the study protocol then exited. They will count towards the enrollment cap of N=30 treated subjects and used in all analyses.

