7.2 Pre-Neurapheresis Imaging (CT) Requirements

As aneurysm securement (especially clipping) may change the amount of blood in the subarachnoid space, a CT is required following aneurysm securement but prior to beginning Neurapheresis. This CT will serve as the Baseline CT (pre-Neurapheresis CT) which, along with the screening CTs, will be compared to the post-Neurapheresis CTs. The Baseline CT is expected to be taken in a department scanner using optimal metal artifact reduction settings at the conclusion of aneurysm securement or following catheter insertion but prior to initiation of Neurapheresis therapy. The baseline CT must be reviewed to determine safety, via intracranial

stability, prior to beginning Neurapheresis therapy. In particular, the Investigator must assess the CT for the following criteria:

- no evidence of re-bleeding;
- no increasing mass effect;
- no effacement of the basilar cisterns;
- continued communication between the ventricles and subarachnoid space

In addition to the CT requirements above, study therapy cannot begin for at least 8 hours following aneurysm securement for subjects who underwent a clipping procedure.

If the subject meets these criteria, study therapy can be initiated. If the subject does not meet these criteria, either the subject can be exited, or another CT can be taken to determine baseline stability. If the subject still does not meet the safety criteria to begin study therapy after the second baseline CT, the subject is to be exited. If the study catheter was not placed prior to the baseline CT, the subject should be exited as an Intent to Treat Subject and no further follow-up is required. If however the study catheter was placed prior to the baseline CT, a 2-day follow-up is to be completed and the subject exited as an Attempt to Treat Subject.

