10.1 Analysis Populations

The following analysis populations will be used to perform the endpoint analyses.

Safety Population:

This population includes only subjects that were classified as Attempt to Treat or Treated Subjects and will be used to analyze all pre-defined safety endpoints.

Treated Population:

This population includes only subjects classified as Treated Subjects and will be used to analyze all pre-defined efficacy endpoints, including exploratory endpoints.

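### A subject with a placed catheter whose therapy never starts has no class in section 5.7.1; section 7.2 covers only some of these subjects, and section 10.1, read literally, leaves the rest out of the Safety Population

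*Combined protocol and SAP*

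**What the plan says.** Protocol section 5.7.1 sorts consented subjects into three classes.

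- Intent to Treat: "Subjects who provide written informed consent but do not have placement of the study catheter attempted".
- Attempt to Treat: those who "have any portion of the catheter placement procedure attempted (including the epidural needle and guidewire) but placement was unsuccessful". The Synopsis gives the same condition ("including the epidural needle and guidewire) but placement was unsuccessful").
- Treated: those who "have successful placement of the study catheter and had Neurapheresis initiated".

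Section 7.2 adds a rule for subjects who do not pass the baseline CT check. A second CT is allowed, and then "If the subject still does not meet the safety criteria to begin study therapy after the second baseline CT, the subject is to be exited". Where the catheter went in before that CT, "a 2-day follow-up is to be completed and the subject exited as an Attempt to Treat Subject". Section 7.4.1 also assigns Attempt to Treat, but only to aborted placement procedures.

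Section 10.1 states that the Safety Population "includes only subjects that were classified as Attempt to Treat or Treated Subjects". Section 10.2 uses that population as the denominator for primary endpoint 2 (related SAEs) and for the secondary safety endpoints. Under the placement endpoint, section 10.2 describes its subjects as those in whom placement was attempted, and again divides by the Safety Population.

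**The concern.** The three classes do not cover every subject who can arise. A subject with a catheter in place and no therapy is not Intent to Treat, because placement was attempted. The subject is not Attempt to Treat as defined, because placement succeeded, and is not Treated, because therapy did not start.

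The protocol's own timetable makes this state foreseeable. Section 7.4 prefers insertion directly after clipping or coiling, while section 7.2 says that "study therapy cannot begin for at least 8 hours following aneurysm securement for subjects who underwent a clipping procedure". Section 7.2 also lets the baseline CT come before insertion, so a subject may pass the CT, have the catheter placed, and still not start.

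Such a subject has been exposed to the needle, the guidewire and the indwelling catheter. Section 6.1 lists risks that can arise from that exposure alone, including CSF leak, infection, subdural spinal hematoma and retained catheter. If the subject has no class, section 10.1 gives no way into the denominator, or the numerator, of the primary safety rate. Section 5.7.1 also states no follow-up for the subject.

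**Working it through.** **Step 1: cross the states with the classes in section 5.7.1.**

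| Attempted | Placed | Therapy started | Class under 5.7.1 |
|---|---|---|---|
| no | no | no | Intent to Treat |
| yes | no | no | Attempt to Treat |
| yes | yes | no | none |
| yes | yes | yes | Treated |

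**Step 2: overlay the other rules on the third row.** Section 7.2 assigns Attempt to Treat to the part of that row where the catheter preceded the baseline CT and the start criteria were not met. Section 7.4.1 assigns nothing here, because its procedures were aborted. What remains is a placed catheter with no start for any other reason: for example, withdrawal or decline after an acceptable CT. Section 10.1 then admits the 7.2 part, if 7.2 governs, and not the remainder.

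**Step 3: inputs for an illustration.**

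- Treated subjects: T = 30 (section 5.7.1).
- Related SAEs among Treated subjects: e = 1. Section 2.2 reports one herniation, classed as serious, among the 16 treated so far. I assume no further SAE among Treated subjects.
- Failed placements: f = 2, assumed.
- Placed, not started and unclassified: k = 1, 3 or 5, assumed. Section 5.7.1 expects up to 40 enrolled for 30 Treated, so at most 40 − 30 = 10 are not Treated; their split is not given.
- SAEs among the k subjects: s = 0 or 1, assumed.

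**Step 4: primary safety rate.** Read literally: e/(T + f) = 1/32 = 3.1%. By exposure: (e + s)/(T + f + k).

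| k | s = 0 | s = 1 |
|---|---|---|
| 1 | 1/33 = 3.0% | 2/33 = 6.1% |
| 3 | 1/35 = 2.9% | 2/35 = 5.7% |
| 5 | 1/37 = 2.7% | 2/37 = 5.4% |

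Omission understates the rate if an omitted subject had an SAE and slightly overstates it if none did.

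**Step 5: placement rate with the same k subjects left unclassified.** Read literally: T/(T + f) = 30/32 = 93.8%. By fact, (T + k)/(T + f + k): 31/33 = 93.9%, 33/35 = 94.3%, 35/37 = 94.6%. The differences are 0.2, 0.5 and 0.8 points.

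**Step 6: how often it might happen.** Section 2.1 reports that PILLAR attempted 14 placements, succeeded in 13, and summarised therapy for all 13. That is 0 of 13 placed and not started. The exact two-sided 95% upper limit is 1 − 0.025^(1/13) = 24.7%, so the observation is reassuring but weak.

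**The case against.** The strongest reply is that the plan already intends an exposure-based population. Section 10.2 treats the Safety Population as the subjects in whom placement was attempted, and the Synopsis explains that Intent to Treat subjects leave at once because they received no part of the catheter or therapy. This stands as evidence of intent. It does not repair section 10.1, which admits subjects by class; it shows that 10.1 and 10.2 disagree.

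A reader might infer that subjects who fail the baseline CT with a catheter in place are dropped. They are not if 7.2 governs: it classifies them as Attempt to Treat, and 10.1 accepts that. The fault there is a label that contradicts its own definition.

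A reader might also infer a large distortion of the placement rate, such as 30/35 (85.7%) against 33/35 (94.3%) at k = 3. That requires success to be scored from the class label, which no section states. It also counts the k subjects inside the placement denominator while the SAE illustration leaves them outside.

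Nor would events escape oversight. Table 4 collects adverse events from catheter placement onward, and sections 13.2 and 13.3 provide for adjudication and DSMB review. What is at risk is the reported rate.

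Some routes to a non-start are narrower than they look. Re-bleeding or mass effect seen on the baseline CT falls under 7.2, and sections 7.4 and 7.4.3 allow one catheter replacement and changes of disposables. Finally, Figure 6 (subject flow) is not shown and may classify these subjects. If it does, the written definitions still need to agree with it.

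**Conclusion.** The concern holds as a fault in the stated classification. Placed-but-not-started subjects have no class in 5.7.1, section 7.2 covers some of them in conflict with that wording, and the literal text of 10.1 excludes the rest. The number affected is unknown and probably small. In a single-arm study of 30 Treated subjects, however, one omitted event can nearly halve the reported SAE rate, while omission without an event barely moves it. This size rests on assumed values of f, k and s. The documents do not support the view that 7.2 subjects are lost from the safety analysis or that the placement rate shifts by more than about a point. The correction should be made before subjects are classified for analysis.

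**What to change.** - **Section 10.1:** define the Safety Population as every enrolled subject in whom any part of catheter placement was attempted. This agrees with section 10.2.
- **Section 5.7.1 and the Synopsis:** define Attempt to Treat as any placement attempt without therapy initiated, whether or not placement succeeded. This agrees with section 7.2.
- **Section 10.2, placement endpoint:** score success from the recorded placement outcome, not from the class. The printed numerator counts subjects attempted; over an attempted-subject denominator it would give 100% by construction, so it must count successful placements.
- **Follow-up:** the sponsor should reconcile the 2-day exit for placed-but-not-started subjects (5.7.1 and 7.2) with the CNS infection endpoint, which runs to 5 days after catheter removal. Without this, the wider population includes subjects not followed through that window.

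The cost is a few sentences and, if the case report forms do not already hold it, one field for placement outcome. The downside is a few more subjects, and possibly events, in the safety rate.
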